4.4.3 LOST TO FOLLOW-UP

A subject will be considered lost to follow-up if the subject cannot be reached after three (3) attempts to contact the subject for a follow-up visit. The site must document a minimum of three (3) attempts, and the final documented attempt should be made via registered letter.

4.4.4 TERMINATION OR SUSPENSION OF STUDY

Revision E: 03Apr2023 Confidential Page **32** of **55**

This study may be suspended or terminated if there is sufficient reasonable cause. Written notification, documenting the reason for study suspension or termination, will be provided by the suspending or terminating party to the investigator, if by the sponsor or regulatory authorities; or the sponsor if by the investigator or the site's IRB. If the study is prematurely terminated or suspended, the PI will promptly inform the IRB and will provide the reason(s) for the termination or suspension.

5 TREATMENT OF SUBJECTS

In this study, subjects undergo screening / baseline evaluation, the study procedure, supplemental embolization procedures as needed and clinical and angiographic follow-up out to 6 months.

Table 6 Schedule of Study Activities by Visit shows the study's visit schedule, allowed windows, and schedule of assessments, which are described in more detail in Sections 5.4 - 5.16.

5.1 SCHEDULE OF EVENTS TABLE

Data will be collected on electronic case report forms at the pre-procedure, at index procedure and post-procedure visits. A schedule of the study activities by visit is provided in Table 6.

PHIL Discharge(s) 30-day Unscheduled Screening / 3-month 6-month Follow-Up1 Baseline procedure(s) follow-up1 Follow-Up1 Hospital visit Assessments Method Office / clinic Office/clinic Office/clinic Office/Clinic Office/clinic/hospital Informed consent Х Assess inclusion / exclusion Х Demographics and medical history Х dAVF information (classification) Χ modified Rankin Scale score Χ NIH Stroke Scale score Х Hunt and Hess Stroke Scale score³ Х Х Physical exam (dAVF symptoms) Х Х Х Χ Χ Χ Χ Clinical chemistry & hematology Х Х Χ Χ QOL (EQ-5D) dAVF and embolized vessel data Χ Irradiation Information Χ PHIL procedure Χ Device usage Χ X^7 X^6 X^8 X^9 Angiography Χ Adverse event / technical event Х Х

TABLE 6 SCHEDULE OF STUDY ACTIVITIES BY VISIT

- 1. Follow-up to be scheduled after completion of the last PHIL treatment.
- 2. Required at any time point if signs of new-onset neurological deficit are present.
- 3. Required in the case of presenting hemorrhage.
- 4. This exam should be completed within 2-days post-procedure.
- 5. To be performed within 7 days in advance of the procedure.
- ${\bf 6.\ DSA\ preferred\ but\ CTA/MRA\ can\ performed\ depending\ on\ subject\ health\ status.}$
- $7. \ Must include a pre-treatment and post-treatment angiogram. \\$
- 8. Required if subject presents with symptoms relating to the treated dAVF (DSA, CTA or MRA acceptable).
- 9. Standard Care imaging (DSA, CTA or MRA acceptable).

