- Subject has severe calcification or vascular tortuosity that may preclude the safe introduction of the sheath, guiding catheter, or access to the lesion with the microcatheter.
- 2. Subject has a contra-indication to DSA, CT scan or MRI/ MRA
- 3. Subject has a history of intracranial vasospasm not responsive to medical therapy
- 4. Subject has extra-cranial stenosis or parent vessel stenosis > 50% proximal to the target lesion to be treated.

Study visits and assessments

	Visits	Screening / Baseline	PHIL procedure(s)	Discharge(s)	30-day follow-up ¹	3-month Follow-Up ¹	6-month Follow-Up ¹	Unscheduled
Assessments	Method	Office / clinic	Hospit	al visit	Office/clinic	Office/clinic	Office/clinic	Office/clinic/hospital
Informed consent		Х						
Assess inclusion / exclu	sion	Х						
Demographics and med	dical history	Х						
dAVF information (class	sification)	Х						
modified Rankin Scale s	score	Х			Х	Х	Х	Х
NIH Stroke Scale score		Х			X ²	X ²	X ²	X ²
Hunt and Hess Stroke S	cale score ³	Х			Х	Х	Х	Х
Physical exam (dAVF sy	mptoms)	Х		X ⁴	Х	Х	Х	Х
Clinical chemistry & her	matology	Х		Х	Х	Х	Х	
QOL (EQ-5D)		Х	⁵				Х	
dAVF and embolized ve	essel data		X					
Irradiation Information			X					
PHIL procedure			X					
Device usage			X					
Angiography	•	X ⁶	X ⁷		X ⁸	X ⁸	Χ	X ⁹
Adverse event / technic	cal event		Х	Х	Х	Х	Х	Х

1 Follow-up to be	scheduled after	completion o	f the la	ast PHIL treatment.	

- 2. Required at any time point if signs of new-onset neurological deficit are present.
- 3. Required in the case of presenting hemorrhage.
- 4. This exam should be completed within 2-days post-procedure.
- 5. To be performed within 7 days in advance of the procedure.
- 6. DSA preferred but CTA/MRA can performed depending on subject health status.
- 7. Must include a pre-treatment and post-treatment angiogram.
- 8. Required if subject presents with symptoms relating to the treated dAVF (DSA, CTA or MRA acceptable).
- 9. Standard Care imaging (DSA, CTA or MRA acceptable).

Statistical analysis:

Descriptive statistics will be used to summarize the data collected in this study.

REVISION HISTORY

Revision	Effective Date
Α	18 Jan 2018
В	26 Apr 2018
С	19 Mar 2020
D	14 Jul 2020
E	03 Apr 2023

SUMMARY OF CHANGES

REVISION D TO REVISION E

Section	Change	Rationale
Protocol Summary,	Added secondary measured outcome: New-onset of device- or	To reflect the correct secondary measured

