3 STUDY DESIGN

3.1 Primary measured outcomes

The following outcomes will be measured:

- Safety: The proportion of subjects with neurological death or ipsilateral stroke within the first 30 days following completion the first PHIL of treatment procedure.
- Probable benefit: Angiographic occlusion of the pre-specified target vessel intended for treatment at procedure following completion of the first PHIL treatment procedure.

Neurologic death is subject death reported as having resulted from a neurologic cause. Stroke is defined as a new focal neurological deficit in a defined vascular distribution of abrupt onset with symptoms persisting for >24 hours AND a neuro-imaging study or other quantitative study that does not indicate a different etiology. This includes ischemic and hemorrhagic strokes. It is expected that fewer than approximately 15% of subjects will experience neurologic death or a stroke within the first 30 days following completion of the first PHIL procedure treatment.

Angiographic occlusion of the pre-specified target vessel is defined as cessation of flow at the point of embolic agent administration at the target vessel. It is expected that approximately 60% of the subjects will achieve cessation of flow of the pre-specified target vessel when treated with PHIL.

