4 SELECTION AND WITHDRAWAL OF SUBJECTS

Subjects who are enrolled in the study but subsequently do not meet the pre-operative inclusion criteria below will not be treated with the PHIL and will be considered enrolled but not treated. These subjects will be considered screen failures, exited from the study, replaced with other subjects that satisfy enrollment and pre-procedural inclusion criteria and will not be included in the analyzed populations.

Before any subject is treated in the study, the screening / baseline angiogram will be reviewed by at least one of the Study Principal Investigators.

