5.5 BASELINE EXAMINATION

Following written informed consent, the study investigator or designee will assess potential study candidates against eligibility criteria. The investigator or designee will record reason for failure in any subject actively considered for study participation.

- Review medical history to determine eligibility based on inclusion/exclusion criteria.
- Review medications history to determine eligibility based on inclusion/exclusion criteria.
- Perform medical examinations needed to determine eligibility based on inclusion/exclusion criteria.
- Schedule study visits for participants who are eligible and available for the duration of the study.
- Provide participants with specific instructions needed to prepare for the procedure.

All baseline examinations will be consistent with standard of care. Subjects who are believed by the investigator to potentially qualify will undergo the following baseline assessments:

- Demographic data
- Medical history, including smoking history
- dAVF information (Borden classification)
- Physical exam to assess dAVF symptoms
- Neurologic assessment by Modified Rankin Scale (mRS) and NIH Stroke Scale
- Hemorrhage assessment by Hunt and Hess Stroke Scale score, if applicable

Angiography

The investigator will document screening and baseline findings in the eCRF. If the subject is found to be ineligible for study participation during the baseline examination, the subject will be notified and exited from the study.

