15 DEFINITIONS

Term	Definition
Adjunctive treatment Adverse Event (AE)	Additional treatments with to continue or complete the treatment of the fistula
	other than PHIL. This could include but is not limited to other liquid embolic agents embolic coils, surgery or radiosurgery.
	Any untoward medical occurrence, unintended disease or injury, or untoward
Adverse event (AE)	clinical signs (including abnormal laboratory findings) in subjects, users or other
	persons, whether or not related to the investigational medical device. (ISC 14155:2011 3.2)
	NOTE 1: This definition includes events related to the investigational medical device
	or the comparator.
	NOTE 2: This definition includes events related to the procedures involved.
	NOTE 3: For users or other persons, this definition is restricted to events related to
	investigational medical devices.
Completion of treatment	Cessation of blood flow through all the vessels targeted for embolization, as specified by treating physician in eCRF.
Concomitant disease-related adverse event	Event is clearly attributable to the underlying concomitant disease state with no
	temporal relationship to the device, treatment, or medication.
Device-related adverse event	Event has a strong temporal relationship to the study device, and alternative
	etiology is less likely.
Enrolled	Subject has provided written informed consent to participate in the study, meets
	all enrollment criteria, and treatment with the PHIL device is attempted. The point
	of enrollment occurs when the PHIL liquid embolic syringe and adaptor assembly is
	connected to the microcatheter hub.
Full Analysis Set Population (FAS)	All enrolled subjects including only those in whom the PHIL™ device was implanted.
NIH Stroke Scale (NIHSS)	Tool to quantify neurological impairment caused by stroke.
Intracranial hemorrhage	Hemorrhage within the fixed vault of the cranium (skull)
Mild	No limitation of usual activities, no therapy or only symptomatic therapy required
(AE severity)	to treat the injury or illness.
Moderate	Some limitation of usual activities or specific therapy is required.
(AE severity)	Some illitation of assault activities of specific therapy is required.
Modified Rankin Scale (mRS)	Scale for measuring general neurologic function.
,	0 No symptoms at all
	1 No significant disability despite symptoms; able to carry out all usual duties
	and activities
	2 Slight disability; unable to carry out all previous activities, but able to look

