#### **4.1 Primary Measured Outcomes**

The following outcomes will be measured:

- Safety: The proportion of subjects with neurological death or ipsilateral stroke within the first 30 days following completion of the first PHIL treatment procedure.
- Probable benefit: Angiographic occlusion of the pre-specified target vessel intended for treatment at procedure following completion of the first PHIL treatment procedure.

Neurologic death is subject death reported as having resulted from a neurologic cause. Stroke is defined as a new focal neurological deficit in a defined vascular distribution of abrupt onset with symptoms persisting for >24 hours AND a neuro-imaging study or other quantitative study that does not indicate a different etiology. This includes ischemic and hemorrhagic strokes.

Angiographic occlusion of the pre-specified target vessel is defined as cessation of flow at the point of embolic agent administration at the target vessel.

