### 8.2 Primary Measured Outcomes

- Safety

The measured safety outcome is the proportion of subjects with neurological death or ipsilateral stroke within the first 30 days following completion the first PHIL of treatment procedure. The descriptive analysis of this outcome will include the number of subjects with neurological death or ipsilateral stroke, the total number evaluated, the percent, and the Clopper-Pearson two-sided 95% confidence limits on the percent.

- Probable benefit

The measured probable benefit outcome is the angiographic occlusion of the pre-specified target vessel intended for treatment at procedure following completion of the first PHIL treatment procedure. The descriptive analysis of this outcome will include the number of subjects with angiographic occlusion of treated vessel at procedure, the total number evaluated, the percent, and the Clopper-Pearson two-sided 95% confidence limits on the percent.

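### The target vessel of the primary benefit outcome is called pre-specified, but no dated entry before embolization is required, and SAP 8.2 counts the treated vessel

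*Protocol*

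**What the plan says.** SAP 4.1 defines the benefit outcome as "Angiographic occlusion of the pre-specified target vessel intended for treatment at procedure following completion of the first PHIL treatment procedure"; Protocol Section 3.1 has the same outcome. Section 3.1 judges occlusion as "cessation of flow at the point of embolic agent administration at the target vessel" and expects it in about 60% of subjects.

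On recording, the protocol says the following:

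- **Baseline (Section 5.5).** The lesion item is "dAVF information (Borden classification"), together with angiography. No target vessel is listed. Section 5.5.3 adds only laboratory tests and the EQ-5D.
- **Schedule (Protocol Summary and Table 6 in Section 5.1).** The one vessel-level row is "dAVF and embolized vessel data". The Protocol Summary copy shows its single mark under the PHIL procedure column.
- **Procedure (Section 5.6).** The investigator records the main features of the device and the procedure. Nothing says that a target must be entered before injection.
- **Definitions (Section 15).** Completion of treatment is "Cessation of blood flow through all the vessels targeted for embolization, as specified by treating physician in eCRF". No time of entry is given.

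SAP 8.2 restates the outcome in terms of the pre-specified target. It then gives the count to be reported as the "number of subjects with angiographic occlusion of treated vessel at procedure".

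**The concern.** A pre-specified target protects the outcome only if the target is on record before anyone knows which vessel closed, and only if scoring uses that record. Here the requirement to record it is missing, and the SAP's counting rule refers to a different vessel.

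The physician who names the target also performs an open-label procedure and sees the result. There is no control arm in which the same latitude would apply. The resulting rate is the headline benefit figure. It will be read against the 60% expectation and, where applicable, against published rates (Protocol 8.2, SAP 8.1). The only item under measures to minimize bias (Protocol 3.5) is a screening log, which does not bear on this.

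The point is when the target is fixed and which vessel is scored. How several target vessels should be combined is a separate question.

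**Working it through.** **1. The plan's own figures.** The stated enrolment reproduces: a loss of 15/75 = 20%, and 60 / (1 − 0.20) = 75. This point does not depend on it. At the expected rate, 0.60 × 75 = 45 subjects are occluded and 30 are not. The Clopper-Pearson 95% limits for 45/75 are 48.0% to 71.1%.

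**2. The texts applied to one subject.** Suppose the intended feeder is A. PHIL is injected into B, and B closes. A was not reached, or is still open.

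- Under SAP 4.1 and Protocol 3.1 the subject is not a success, provided A is on record as the target.
- If A was never reached, there is no point of administration at A, so the flow criterion cannot be applied to it. No rule says that such a vessel counts as not occluded.
- Under the SAP 8.2 count, B is the treated vessel and it closed, so the subject is a success.

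The same subject is therefore scored differently under SAP 4.1 and SAP 8.2. The case concerns subjects in whom PHIL was implanted somewhere; those with no implant are outside the Full Analysis Set (SAP Section 7).

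**3. Whether another provision fixes the target first.**

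- Section 4: "the screening / baseline angiogram will be reviewed by at least one of the Study Principal Investigators" before treatment. Recording a target at that review is not mentioned.
- Schedule footnote 7: imaging at the procedure "Must include a pre-treatment and post-treatment angiogram". An entry before injection is possible, but none is required.
- Section 7.4: an independent committee adjudicates the primary outcomes. No dated target is supplied for it to adjudicate against.
- Section 12.1: the EDC time-stamps changes. This shows when an entry was made but does not require it before embolization.

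**4. Scale, under an assumption.** Let g be the share of subjects with a non-occluded intended target who are nevertheless counted as successes, because another treated vessel closed or because the target was named afterwards. With 60% true occlusion in 75 subjects:

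reported rate = 60% + 40% × g

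| g (assumed) | Extra successes (30 × g) | Reported rate |
|---|---|---|
| 0 | 0 | 60% |
| 0.10 | 3 | 64% |
| 0.25 | 7.5 | 70% |
| 0.50 | 15 | 80% |

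The documents give no value for g. It cannot exceed the share of failures in which a second vessel was treated and closed, and that share is not given either.

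**The case against.** The strongest reply is that the outcome definition itself says the target is pre-specified, so naming it afterwards would breach the protocol. On this view, SAP 8.2 uses treated vessel as shorthand for the target it named one sentence before. The eCRF pages are not public, and Section 5.1 says that data are also collected before the procedure, so a pre-procedure target field may exist. The procedure visit includes a pre-treatment angiogram. A Study Principal Investigator reviews the baseline angiogram, all procedure images go to the sponsor, and independent physicians adjudicate. The study is descriptive, with no success threshold to cross.

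Much of this stands, and it limits what can be said. A reader might infer that the target is recorded nowhere before the procedure, or that the operator names it already knowing the result. The documents do not support either inference: they are silent on timing, and an entry before injection is compatible with them. Nor do they show that the rate is biased upward, only that such bias is not excluded. It would also be wrong to say that the data could never reveal late naming, since the audit trail may show it.

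Two things remain. None of these safeguards requires a target to be fixed before injection. And the SAP 8.2 wording differs from SAP 4.1 whatever the eCRF contains. If it is shorthand, correcting it costs nothing.

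**Conclusion.** The point holds in this form: the documents do not require a dated record of the target vessel before embolization, and the SAP 8.2 numerator does not match the outcome in SAP 4.1. The mismatch is the firmer part, because it rests on the text alone. The timing gap rests on the absence of a requirement in the available documents; the eCRF could narrow it.

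Any bias would be upward, since the looser count can add successes but not remove them. Its size cannot be derived. On the assumptions of 60% true occlusion and 75 evaluated subjects, every 10% of failures counted as successes adds 4 percentage points (3 subjects). At g = 0.25 the shift of 10 points approaches the 11.1-point distance from 60% to the upper confidence limit. The interval would not reflect such a shift. The matter should be settled before the primary benefit rate is reported, but it does not invalidate the study.

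**What to change.** 1. In Protocol 5.5 or 5.6 and in the schedule, require a time-stamped eCRF entry of the target vessel(s) for the first PHIL procedure before the first injection. The natural moment is the Study Principal Investigator's angiogram review, with an update allowed after the pre-treatment angiogram.
2. Have the Section 7.4 committee score occlusion against that entry.
3. In SAP 8.2, replace the treated vessel with the pre-specified target vessel, and state that an intended vessel not reached or not occluded counts as not occluded.
4. List every subject whose embolized vessel differs from the target.
5. For subjects already treated, report from the EDC audit trail how many targets were entered before the procedure.

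The cost is an eCRF field with a timing rule, short edits to the protocol and SAP, one listing and one audit-trail query. Treatment is unaffected. The downside is that the reported occlusion rate may be slightly lower.

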5.7 DISCHARGE EXAMINATION

The subject is discharged from the hospital after standard post-procedure recovery. The subject will have a physical exam to assess dAVF symptoms; this exam should be completed within 2-days post-procedure. The investigator/designee will collect routine post-procedure routine clinical chemistry and hematology labs before

discharge, record discharge status information, including hospital length of stay, and occurrence of any postoperative adverse events in the eCRF.

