5.9 FOLLOW-UP

Subjects will undergo follow-up at a location designated by the research staff at 30 days, 3 months and 6 months following completion of treatment. The investigator will document all findings in the eCRF.

5.9.1 30 DAY (-14 / +14 DAYS)

This visit is to be conducted 30 days following completion of the last PHIL treatment. At this visit, the subject will undergo

- Neurological assessment by Modified Rankin Scale (mRS)
- Neurological assessment by NIH Stroke Scale (if applicable)
- Hemorrhage assessment by Hunt and Hess Stroke Scale (if applicable)
- Assessment dAVF symptoms

- Collection of routine clinical chemistry and hematology labs.
- Record adverse events as reported by participant or observed by investigator.
- Angiographic assessment if the subject presents with symptoms relating to the treated dAVF (DSA, CTA or MRA is acceptable).

5.9.2 3 MONTH VISIT (-2 / + 4 WEEKS)

This visit is to be conducted 3 months following completion of the last PHIL treatment. At this visit, the subject will undergo

- Neurological assessment by Modified Rankin Scale (mRS)
- Neurological assessment by NIH Stroke Scale (if applicable)
- Hemorrhage assessment by Hunt and Hess Stroke Scale (if applicable)
- Assessment dAVF symptoms
- Collection of chemistry and hematology labs
- Record adverse events as reported by participant or observed by investigator.
- Angiographic assessment (if applicable)

5.9.3 6 MONTH VISIT (-3/+6 WEEKS)

This visit is to be conducted 6 months following completion of the last PHIL treatment. At this visit the subject will undergo

- Neurological assessment by Modified Rankin Scale (mRS)
- Neurological assessment by NIH Stroke Scale (if applicable)
- Hemorrhage assessment by Hunt and Hess Stroke Scale (if applicable)
- Physical exam to assess dAVF symptoms
- Collection of chemistry and hematology labs
- Subject self-reported QOL questionnaire using EQ-5D
- Record adverse events as reported by participant or observed by investigator.
- Angiographic assessment

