5.14 STANDARD OF CARE PROCEDURES

The following procedures and/or assessments that will be completed during the study are considered standard of clinical care.

- Review medical history
- Fistula classification
- CT angiography / MR angiography
- Embolization to occlude blood vessels
- Neurologic assessment with modified Rankin Scale
- Neurologic assessment with NIH Stroke Scale
- Hunt and Hess Stroke Scale score
- Clinical chemistry and hematology before the procedure, after the procedure and at 6 month follow-up.

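### Primary safety counts strokes of any severity, but no neurological scale is scheduled at the procedure or discharge, and NIHSS after baseline is required only once a deficit has been noticed

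*Protocol*

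**What the plan says.** Protocol 3.1 and SAP 4.1 define the primary safety outcome as neurological death or ipsilateral stroke "within the first 30 days following completion of the first PHIL treatment procedure". Stroke is a "new focal neurological deficit in a defined vascular distribution of abrupt onset with symptoms persisting for >24 hours", supported by imaging or another quantitative study that does not point to a different cause. The definition has no severity threshold.

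Protocol 5.5 requires at baseline "Neurologic assessment by Modified Rankin Scale (mRS) and NIH Stroke Scale". After the procedure, Protocol 5.7 says: "The subject will have a physical exam to assess dAVF symptoms; this exam should be completed within 2-days post-procedure". It adds laboratory tests and recording of postoperative adverse events. Section 5.8.1 repeats this after each supplemental procedure. The schedule in the Protocol summary has no mRS or NIHSS entry under the procedure or discharge columns.

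For NIHSS after baseline, footnote 2 to the schedule reads "Required at any time point if signs of new-onset neurological deficit are present", and section 5.9 lists the scale at each follow-up visit only where applicable. The mRS is unconditional at 30 days, 3 months and 6 months. The 30-day visit is timed from the last PHIL treatment, with a window of 14 days either side.

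**The concern.** A stroke enters the primary outcome only if someone notices a new focal deficit, establishes that it outlasted 24 hours, and obtains a study to support the diagnosis. The plan leaves the first step to an exam described in terms of dAVF symptoms and to adverse event reporting, in an open-label, single-arm study. A mild deficit that lasts several days and clears before the 30-day visit meets the definition, yet nothing scheduled is designed to pick it up.

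The error would probably run one way. A missed stroke lowers the reported rate, and that rate is read against the Protocol's own expectation of fewer than about 15% and, under Protocol 8.2 and SAP 8.1, against rates in the literature. The missing-data methods in SAP 8.6 do not help. A subject with an unrecognised stroke has no missing value; the subject is recorded as event-free.

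**Working it through.** **1. The plan's own figures.** Protocol 8.1 and SAP 6 enrol 75, allow 15 lost, and expect 60 with 6-month follow-up. Check: 60 / (1 − 15/75) = 60 / 0.80 = 75. This reproduces. The figures serve below only as denominators; the point itself rests on reading the schedule.

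**2. Scheduled assessments, side by side** (Protocol summary schedule; sections 5.5 to 5.9).

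| Time point | mRS | NIHSS | Other relevant items |
|---|---|---|---|
| Baseline | yes | yes | physical exam |
| Each PHIL procedure | no | no | angiograms before and after treatment; before a supplemental procedure, a dAVF-symptom exam and labs |
| Each discharge | no | no | dAVF-symptom exam within 2 days, labs, adverse events |
| 30 days after last treatment | yes | only with signs of new deficit | dAVF symptoms, labs, adverse events; angiography only if symptomatic |

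Hunt and Hess scoring applies only to presenting hemorrhage and is not scheduled at discharge either. The schedule lists no routine brain imaging for stroke after treatment.

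**3. Timing of the discharge exam.** It may take place at any time up to 2 days, so it can precede the 24 hours that the stroke definition requires. A deficit seen then cannot yet be classified, and the next scheduled scale is at the 30-day visit.

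**4. Where the 30-day visit falls.** Let d be the number of days from the first to the last PHIL treatment.
- The visit falls between d + 16 and d + 44 days after the first procedure.
- With one procedure (d = 0), that is day 16 to day 44. The first scheduled scale may therefore come before or after the primary window closes.
- The visit can fall inside the 30-day window only if d + 16 ≤ 30, that is, d ≤ 14.
- If the last treatment is more than 14 days after the first, no scale is scheduled between the first procedure and day 30. Section 5.8 foresees up to seven procedures at the physician's discretion and lists no scale before a supplemental one.

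**5. What one missed event is worth.** One event is 1/75 = 1.3 points, or 1/60 = 1.7 points. SAP 8.2 reports two-sided 95% Clopper-Pearson limits: the lower limit is the 0.025 quantile of Beta(x, n − x + 1), the upper the 0.975 quantile of Beta(x + 1, n − x).
- n = 75: 5 events give 6.7% (2.2 to 14.9); 6 events give 8.0% (3.0 to 16.6).
- n = 60: 3 events give 5.0% (1.0 to 13.9); 4 events give 6.7% (1.8 to 16.2).

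At those counts, one missed stroke moves the upper limit from above 15% to below it.

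**6. Illustration with an assumed detection rate.** The documents give no detection rate, so s below is purely an assumption. Observed rate = true rate × s.

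| True rate | s = 100% | 90% | 80% | 70% | 50% |
|---|---|---|---|---|---|
| 15% | 15.0% | 13.5% | 12.0% | 10.5% | 7.5% |
| 10% | 10.0% | 9.0% | 8.0% | 7.0% | 5.0% |

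Here s applies to the whole composite. Deaths and disabling strokes would hardly be missed, so the low end would require most events to be mild.

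**The case against.** The strongest reply is that the period is not unobserved. A post-procedure exam is scheduled within 2 days, and adverse events are collected from enrolment with onset and resolution times. At the 30-day visit events are recorded from the subject's report as well as the investigator's observation, so a resolved deficit can still be captured by history. Visits related to the treated dAVF or a possibly associated event should include a neurologic examination using mRS (5.10). At least three independent physicians adjudicate the outcomes (7.4). Footnote 2 applies at any time point, so a deficit recognised at discharge does trigger NIHSS. Section 5.14 also lists "Neurologic assessment with NIH Stroke Scale" as standard of care, so some sites may do it anyway.

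All of this stands and limits the concern, but it does not remove it. The exam may come too early to judge persistence. The mRS measures general function, so a mild focal deficit need not change it. Adjudication can act only on events that reach the committee. Listing a scale as standard of care does not schedule it.

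Three stronger readings are tempting, and the documents do not support them.
- A reader might infer that detection rests wholly on chance recognition. The safeguards above show otherwise.
- A reader might infer from Table 2 that the exam would miss sensory or cerebellar deficits such as those in Table 5. Table 2 is background on presentation; the Protocol nowhere uses it to define the exam.
- A reader might call the NIHSS rule self-contradictory. Examining first and scoring afterwards is a coherent two-step design, and the stroke definition does not depend on an NIHSS score. The weakness is only that the first step is not standardised.

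**Conclusion.** The point holds as a weakness in ascertaining the primary safety outcome. Followed as written, the plan can leave a qualifying mild stroke unrecorded, and a subject whose last treatment comes more than 14 days after the first has no scheduled neurological scale inside the primary window.

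The likely direction is under-counting. The size is unknown: each missed event is worth 1.3 points at N = 75, and nothing in the documents says how many, if any, would be missed. The 15% figure is an expectation in the Protocol, not a success criterion. The study is descriptive and no formal test is affected. The conclusion assumes that sites do what the schedule requires and no more; sites that routinely score NIHSS after embolization would have a smaller gap. The telephone visits allowed under 5.12 during the pandemic would have made it larger for the subjects concerned.

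**What to change.** In Table 6 and sections 5.7, 5.8, 5.8.1 and 5.9.1, make NIHSS unconditional at these points:
- before each supplemental PHIL procedure, as a fresh comparator (the baseline score serves for the first procedure);
- at the post-procedure or discharge assessment after each PHIL procedure, timed beyond 24 hours where the subject is still in hospital;
- at the 30-day visit, with an added assessment at about day 30 after the first procedure in staged subjects, combined with a supplemental-procedure visit where possible.

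Send any increase over the pre-procedure score to the Data Safety and Outcomes Monitoring Committee for stroke adjudication. For subjects already treated, report how many had an NIHSS inside the primary window and state the limitation next to the primary safety rate.

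The cost is a short scale, already performed at baseline, repeated at each procedure and at 30 days, with an occasional extra assessment in staged subjects. There will be more minor deficits to adjudicate, and the reported stroke rate may be slightly higher. A stroke that arises after discharge and clears before the next assessment would still depend on history, so the change narrows the gap without abolishing it.
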